Study Protocol and Statistical Analysis Plan

A Study to Compare Patient Perceptions of Two Different Hearing Aid Processing Philosophies

Version 1.0

September 13 2021

NCT04839289

Protocol Title

1 Background

Hearing aid brands vary in their DSP (Digital Signal Processing) strategies. For example, there are philosophical differences in processing when there is uncertainty of target location. One processing strategy aligns with a front facing target, whereas another aligns with the absence of a target in these situations. Despite the investigations regarding the different processing strategies, research has been limited as to how different populations perceive these different strategies in their daily life. Previous data gives insight to the different strategies in lab environments and simulated acoustic environments, but there is substantial need to investigate how these findings relate to the real world, which this study seeks to accomplish through the use of a home trial comparison.

2 Objectives

The primary objective of this study is to investigate whether individuals with moderate to severe hearing loss perceive a difference between Brand A and Brand B devices in their daily life.

3 Description of the investigational device

The investigational devices are intended for consumers with hearing loss, and provide amplification for soft, medium, and loud inputs using varying methods of compression and features. The devices will be used as intended for this investigation.

4 Design of the clinical investigation

This interventional study uses a within-subject, single blinded design with three conditions: Condition one consists of study hearing aid set A, condition two is study hearing aid set B, and condition three is study hearing aid set C. Sets A and C are the same hearing aids but will be different color casings. Twenty participants are planned.

5 Risks and benefits of the investigational device and clinical Investigation

Hearing aids enable people to hear sounds again, which could not be heard previously due to a hearing loss. The benefit of a compensated hearing loss results in a facet of multiple benefits which can be measured in different dimensions.

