One of the main benefits of hearing aids is that they may enable people with a hearing loss to better and easier hear speech again, which is a fundamental ability to communicate and interact with others (e.g. family and friends, colleagues at work) in different listening situations in daily life.

The investigation carries risks typical to the standard of care for fitting and placing hearing aids in the ear. When placing a dome in the auditory canal, there is the risk of discomfort to the participant. There are risks of skin sensitivity to the material of the devices inserted into the auditory canal and behind the ear (pinna).

The risks of this study are minimal as the procedures are within the scope of practice of the

research audiologists. The participants may notice an improvement in hearing as compared to their own devices, or they may prefer their own devices to the study devices. The primary endpoint of subjective questionnaires and calculation of the Net Promoter Score will provide evidence for the perceived similarities or differences between the two study devices, as well as any preference for either device.

6 Endpoints

- SSQ (Speech Spatial Qualities) Questionnaire: Subjective ratings from 0 to 10 on various aspects of hearing aid performance in daily life, hearing speech in a variety of situations and contexts, spatial hearing, and overall qualities of hearing.
- Hearing Aid Satisfaction Score: Subjective ratings on overall satisfaction of devices. Ratings range from Very Satisfied (5) to Very Dissatisfied (1) for a number of hearing aid features, as well as performance in various listening situations.

7 Inclusion and Exclusion Criteria

Inclusion criteria for participant selection:

1. Experienced (6+ months) Phonak hearing aid users
2. N3-N4 binaural sensorineural hearing loss
3. Age 18 years and older

Exclusion criteria:

1. Conditions which may cause fluctuations in hearing (i.e. Meniere's)
2. Unable to tolerate the physical fit of RIC device with standard fit domes
3. Unable or unwilling to wear study devices for specified period of time, or inability to be seen for 4 study visits

8 Measurements and procedures

This study has a total of four visits.

Visit 1	Visit 2 (following Home Trial #1)	Visit 3 (following Home Trial #2)	Visit 4 (following Home Trial #3)

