-Sound Quality Questionnaire for own devices -Hearing Aid Satisfaction survey for own devices -Three sets of hearing aids programmed for participant -Participant leaves with set A for home trial #1	-Sound Quality Questionnaire for Set A -Hearing Aid Satisfaction survey for Set A -Participant returns Set A and is sent home with Set B for home trial #2	-Sound Quality Questionnaire for Set B -Hearing Aid Satisfaction survey for Set B -Participant returns Set B and is sent home with Set A (Participant is told this is set C) for home trial #3	-Sound Quality Questionnaire for Set A -Hearing Aid Satisfaction survey for Set A -Participant returns set A and exits study

9 Statistical design and analysis

Fifteen to twenty participants are needed to determine significant differences between the study set A device and study set B device algorithms and sound quality. As the null

hypothesis (no difference will be detected) is the expected outcome, a smaller number of participants is acceptable. As this is an exploratory study, no a priori power analysis has been done.

Data collection will terminate once the acceptable number of participants has been recruited and have completed all three trials. As this is an observational study and done for internal purposes only, there is no statistical criteria for termination.

There are no planned objective tests for this study, therefore, all data collected will be subjective and qualitative in nature. Responses will be collected as question, response, and anonymous participant ID.

Responses to the subjective questionnaires will be analyzed using a repeated measures ANOVA test. The mean scores for each subsection of the sound quality questionnaire will be analyzed between the three test devices for all participants. The mean scores of each subsection of the sound quality questionnaire will also be analyzed between the three sets of study devices for all participants. Repeated measures ANOVA will also be used to determine if there are any individual differences between the brands. Aggregate data and individual HASS data will be analyzed using repeated measures ANOVA.

10 Investigation Duration

The expected duration of participation is six weeks.

11 Data Handling and Management

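### No visit lists a direct difference or preference question, although these are the stated objective and promised evidence, and no A-versus-C contrast is pre-specified to calibrate the A–B difference

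*Combined protocol and SAP*

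**What the plan says.** Section 2 gives one objective, labelled primary: whether people with moderate to severe hearing loss "perceive a difference between Brand A and Brand B devices in their daily life". Section 5 names the evidence: "The primary endpoint of subjective questionnaires and calculation of the Net Promoter Score will provide evidence for the perceived similarities or differences". The same sentence extends this to a preference for one device over the other.

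Section 6 lists two endpoints, both absolute ratings. The SSQ is described as "Subjective ratings from 0 to 10 on various aspects of hearing aid performance in daily life". For the Hearing Aid Satisfaction Score, "Ratings range from Very Satisfied (5) to Very Dissatisfied (1) for a number of hearing aid features".

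Section 4 says that sets A and C are the same aids in differently coloured casings. In the Section 8 table, participants rate their own devices at Visit 1, set A at Visit 2, set B at Visit 3, and set A again (presented to them as set C) at Visit 4. The last entry is "Sound Quality Questionnaire for Set A -Hearing Aid Satisfaction survey for Set A -Participant returns set A and exits study".

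Section 9 compares subsection means across the three sets by repeated measures ANOVA and uses the same method for aggregate and individual satisfaction data. It expects no difference to be detected, and states that the study is exploratory and that no power analysis was done.

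**The concern.** Participants are never scheduled to be asked the question that the study is meant to answer. Perception and preference have to be deduced from absolute scores given at separate visits, roughly two weeks apart if the six weeks of Section 10 are split evenly over three home trials (my assumption; the length of each trial is not stated).

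Absolute scores are an imperfect proxy. Someone who clearly hears a difference may still give both sets a 4 for satisfaction. Someone who hears none may move from 4 to 5 between visits. Means can also hide opposing views: if 10 of 20 participants score A one point higher and the other 10 score B one point higher, the mean difference is (10 × 1 − 10 × 1)/20 = 0.

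Because the expected outcome is a null result, a null on mean ratings could be reported as participants perceiving no difference when none of them was asked. The disguised repeat of A shows how far ratings move when the device has not changed, but the plan does not say how that information will be used.

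**Working it through.** This is mainly a comparison of sections. The plan gives no figure to reproduce: 15 to 20 participants is stated without alpha, power, effect size or standard deviation.

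**1. What is promised against what is collected**

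| Item | Section 5 | Section 6 endpoint | Section 8 visit | Section 9 analysis |
|---|---|---|---|---|
| Per-set questionnaire ratings | yes | yes | Visits 1 to 4 | ANOVA |
| Net Promoter Score | yes | no | none | none |
| Direct difference question | not named | no | none | none |
| Preference | yes | no | none | none |

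Preference is promised, and its only named sources are the questionnaires, described as absolute ratings, and a score that is never scheduled. (Section 8 calls the first instrument a sound quality questionnaire; I take it to be the SSQ of Section 6.)

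**2. What the disguised repeat gives**

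Set C is rated on both instruments at Visit 4 and is one of the three ANOVA levels, so A–C rating differences will exist. However, the three-level omnibus test addresses A = B = C. Rejection does not show which pair differs, and no A–C contrast or rule for reading A–B against A–C is stated.

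The order is fixed. Let *a* and *b* be the device effects, and suppose a linear period effect of *p* per home trial (assumed):

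- A = a + p, B = b + 2p, C = a + 3p
- C − A = 2p
- B − A = (b − a) + p
- C − B = (a − b) + p
- B − (A + C)/2 = (b + 2p) − (a + 2p) = b − a

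So A–C measures period change as well as rating noise, and A–B is confounded with period. B against the mean of A and C removes a linear trend, but not any other.

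**3. What the planned size can show** (assumed two-sided alpha 0.05)

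*Existing ratings.* Paired t-test, 80% power (assumed), noncentral t: the smallest detectable A–B difference is 0.78 SD of the paired differences at n = 15 and 0.66 SD at n = 20.

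*A two-way preference item.* Exact binomial test against 50%; *r* is the smallest count with P(X ≥ r | n, 0.5) ≤ 0.025:

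- n = 15: r = 12, two-sided p = 2 × 576/32,768 = 0.035
- n = 20: r = 15, two-sided p = 2 × 21,700/1,048,576 = 0.041

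Power is P(X ≥ r | n, π) for true preference π:

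| True preference | n = 15 | n = 20 |
|---|---|---|
| 60% | 9% | 13% |
| 70% | 30% | 42% |
| 80% | 65% | 80% |
| 90% | 94% | 99% |

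These figures assume that everyone states a preference. If 5 of 20 answer that they have none, the test has 20 − 5 = 15 answers and the n = 15 column applies. Exact 95% intervals near an even split are wide: 7 of 15 gives 21% to 73%, and 10 of 20 gives 27% to 73%.

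**The case against.** The sponsor chose to infer perceived difference from single-blinded, repeated ratings, and Section 5 says so. On that view a direct question is a reviewer's preference, in a study that is exploratory and for internal use. Much of this stands. A reader might infer that the objective cannot be addressed at all; the documents do not support that, because the ratings address it indirectly. Section 9 also mentions individual differences between brands and individual satisfaction data, although it gives no threshold for calling a person's ratings different.

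A reader might also infer that the disguised repeat is not used as a control. That does not follow either: set C is rated on both instruments and analysed with the other two sets. What is missing is a pre-specified contrast and a reading rule.

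The questionnaire items are not reproduced, so a comparative item inside one of them cannot be excluded. The point is therefore that no visit lists such an item. Both instruments are, however, described as absolute ratings and are given one set at a time.

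Two objections to adding a question are sound and shape the fix. Sets A and C differ in colour, so an unrestricted question about noticing a difference can truthfully be answered yes. And a question at Visit 3 could prompt participants to look for differences in set C, altering the ratings of the repeat.

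What the objection does not answer is preference. Section 5 promises it, and no scheduled item, endpoint or analysis supplies it directly.

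**Conclusion.** The point holds as a gap in measurement and specification. As written, the plan lists 0 direct comparisons from up to 20 participants, although its objective is comparative. The gap is clearest for preference, which has no dedicated source, and weaker for perceived difference, which the ratings reach indirectly. The A–C information will be collected, but without a stated use.

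The ratings remain usable, so this is a worthwhile low-cost improvement and not a fatal flaw. Nor would a direct question give the study adequate power: on the assumptions above, only a preference of about 80% or more would be detected with 80% power at n = 20, and at n = 15 power at 80% preference is 65%. The verdict assumes that the questionnaires contain no comparative item.

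**What to change.** **Section 8, Visit 4 only.** After the set C questionnaires and before any debriefing, ask for B versus C and for A versus C: *Apart from colour or appearance, did you notice a difference in sound or hearing? Which do you prefer for hearing, or no preference?* Asked last, it cannot affect any rating. Do not ask it at Visit 3.

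**Sections 6 and 9.** List perceived difference and preference as exploratory outcomes. Report counts and percentages with exact confidence intervals, descriptively.

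**Section 9.** Pre-specify the A–C contrast on the existing ratings, and state that the A–B and B–C differences will be read against it. B against the mean of A and C can be added, noting that it removes a linear period trend only.

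**Section 5.** Point to the new items as the source of preference evidence, and either schedule and define the Net Promoter Score or delete it.

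**Cost and limits to state.** About one minute at Visit 4 and a simple tabulation, with no extra visits or participants. The A–C answer relies on recall across the intervening home trial. Because the order is fixed, A–C also carries change between home trials 1 and 3, so it is an imperfect control on false reports. The B–C answer compares consecutive trials, but always with B first.

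### Section 9 accepts a smaller sample because a null result is expected and calls 15 to 20 participants necessary without a power analysis; a non-significant ANOVA cannot by itself show the similarity named in Section 5

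*Combined protocol and SAP*

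**What the plan says.** The Section 2 objective is to "investigate whether individuals with moderate to severe hearing loss perceive a difference between Brand A and Brand B devices in their daily life". Section 4 plans 20 participants.

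Section 9 makes three statements about sample size in one paragraph:

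- "Fifteen to twenty participants are needed to determine significant differences between the study set A device and study set B device algorithms".
- A reduced number is tolerable because the null "hypothesis (no difference will be detected) is the expected outcome, a smaller number of participants is acceptable".
- Because the study is exploratory, "no a priori power analysis has been done".

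The rule for ending recruitment, also in Section 9, is "Data collection will terminate once the acceptable number of participants has been recruited and have completed all three trials". The only inferential method is given there too: "Responses to the subjective questionnaires will be analyzed using a repeated measures ANOVA test".

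Section 5 expects more than a test of difference: "The primary endpoint of subjective questionnaires and calculation of the Net Promoter Score will provide evidence for the perceived similarities or differences".

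Everyone follows the same order. In the Section 8 visit table, the entry for Visit 3 reads "Participant returns Set B and is sent home with Set A (Participant is told this is set C) for home trial #3", so the sequence is A, B, A for all participants.

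**The concern.** The expected-null reason treats a small sample as safe when no difference is anticipated. If the brands are truly alike, sample size does not change the false-positive rate of a 5% test, so a small study gains nothing. If they differ, a small study is more likely to miss it. If the aim is to support similarity, a small study gives a wider interval and so weaker support.

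The statement that 15 to 20 are needed to find significant differences implies a calculation that the same paragraph says was not made.

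The result the plan expects is a non-significant ANOVA, and no rule says how it will be reported. Without an interval or a margin, a finding that the brands are close and a finding too imprecise to tell would look the same in the report. The rationale also reaches study conduct, because recruitment ends at a number described only as acceptable.

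**Working it through.** **The plan's own figure.** The range 15 to 20 cannot be reproduced: no significance level, power, effect size or SD is given. Working backwards for a paired two-sided 5% test with 80% power (both assumed), the noncentral t gives a detectable difference of 0.78 SD of the paired differences at n=15 and 0.66 SD at n=20. Nothing in the documents says that either was the target.

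**Inputs.** From the documents: 15 to 20 participants (Section 9), 20 planned (Section 4); three conditions in the order A, B, A with the last labelled C (Sections 4 and 8); repeated measures ANOVA (Section 9). Assumed for illustration: two-sided 5%; differences in units of the SD of a single A–B difference, so the condition error variance is 0.5; equal variances and correlations; no period effect except where stated; each endpoint taken alone without multiplicity adjustment.

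**Step 1. Chance of a non-significant ANOVA.** The F test has 2 and 2(n−1) degrees of freedom. With means (0, d, 0) the noncentrality is n × (2/3) × d² / 0.5. At d=0 it is zero, so the test is non-significant 95% of the time at every n. At d=0.5 it is n × (2/3) × 0.25 / 0.5 = n/3.

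| n | Noncentrality at d=0.5 | Non-significant, d=0 | Non-significant, d=0.5 |
|---|---|---|---|
| 10 | 3.33 | 95% | 70% |
| 15 | 5.00 | 95% | 54% |
| 20 | 6.67 | 95% | 40% |
| 30 | 10.00 | 95% | 21% |

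Only the last column moves with n.

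**Step 2. The condition on the 95%.** It requires no period effect, because period and device are tied together by the fixed order. Suppose ratings step up by 0.4 SD after period 1 and then stay level, with identical brands. The means are (0, 0.4, 0.4), the noncentrality is n × (2/3) × 0.16 / 0.5 = 0.2133n, and the ANOVA is non-significant in about 69%, 59% and 41% of studies at n=15, 20 and 30. This qualifies the 95% figure; it gives no support to choosing a small n because a null is expected.

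**Step 3. Precision of the brand contrast.** Take Set B minus the mean of Sets A and C. Let r be the correlation between different devices and rAC that between the two periods with the same device. The variance is s²[1 + (1 + rAC)/2 − 2r], with s² = 1/[2(1 − r)]. It equals 0.75 when rAC = r and 1.00 when rAC = 1. The 95% half-width is t(0.975, n−1) × √(variance/n):

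- n=20: 2.093 × √(0.75/20) = 0.41, up to 2.093 × √(1.00/20) = 0.47.
- n=15: 2.145 × √(0.75/15) = 0.48, up to 2.145 × √(1.00/15) = 0.55.

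Period means (p1, p2, p3) shift this contrast by p2 − (p1 + p3)/2. A linear trend (0, q/2, q) gives zero. A step that then stays level (0, q, q) gives q/2, so a 0.4 SD step shifts it by 0.2 SD.

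**Step 4. What a similarity rule would demand.** Suppose a margin of ±0.5 SD (assumed) and require the 90% confidence interval to lie inside it. With a true difference of zero, the rule fails 40% (variance 0.75) to 61% (variance 1.00) of the time at n=20, and 62% to 80% at n=15.

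**The case against.** The strongest defence is one of scope. The study is labelled exploratory, says openly that there was no power analysis, and is to be documented in an internal report only (Section 19). Its objective is to detect a difference, which ANOVA fits. Similarity is a single word in the risks-and-benefits section. The repeated Set A also offers a within-device reference against which an A–B difference could be judged. All of this stands and limits the severity. It does not make the expected-null reason correct, and the plan does not say that the A–C comparison will serve as such a reference.

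A reader might infer more than the documents support:

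- *That omitting a power analysis is itself an error.* In a declared exploratory study it is not. The faults are the reason given for a small sample and the claim that 15 to 20 are needed.
- *That the sponsor will declare the brands equivalent from a non-significant test.* No passage commits to that. The plan simply does not say how such a result will be read.
- *That recruitment may stop below 15.* The reference to a smaller number can equally describe 15 to 20 itself.
- *That Section 4 promises 20 completers.* It gives 20 as the planned number; the completion condition is in Section 9.
- *That the Net Promoter Score belongs to this point.* Its lack of an analysis in Section 9 is missing detail and is not part of this conclusion.

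**Conclusion.** The point holds, with limited reach, and should be fixed. The expected-null rationale is wrong as written, and that conclusion needs none of the assumed figures. The statement that 15 to 20 are needed has no stated basis. The inferential gap concerns only the similarity conclusion: a non-significant ANOVA alone cannot support it.

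The sizes are illustrations in units of the SD of a single A–B difference, since the documents give no SD, effect size, significance level or margin. At the sample sizes in the plan, a true 0.5 SD difference would be missed in roughly half of studies (54% at n=15, 40% at n=20), and the brand contrast would be known to within about 0.41 to 0.55 SD. A reader might go on to infer that the study is invalid. The documents do not support that: given its exploratory and internal purpose, what is limited is the conclusion that a null result can carry.

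**What to change.** 1. In Section 9, delete the sentence that accepts a smaller sample because the null is expected, and the claim that 15 to 20 are needed to find significant differences. Insert: *The plan is for 20 participants (Section 4), with 15 to 20 completers accepted. This is a feasibility number and was not based on a power calculation.* In the termination sentence, refer to this range in place of an unspecified acceptable number.

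2. Insert in Section 9: *For each questionnaire subsection and for HASS, Set B minus the mean of Sets A and C, and Set A minus Set C (same device), are reported with 95% confidence intervals, without multiplicity adjustment. A non-significant ANOVA is not by itself evidence of no difference or of similarity. No similarity claim is made unless a margin was fixed and justified before data review and the 90% confidence interval lies inside it.*

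3. State the expected precision of the B contrast in units of the SD of a single A–B difference: a 95% half-width of about 0.41 to 0.47 at 20 completers and 0.48 to 0.55 at 15. Add that under the fixed A, B, A order only a linear period trend cancels.

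4. If no margin is set, drop the word *similarities* from the Section 5 sentence and keep *differences*.

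The cost is wording plus two contrasts with intervals per subsection and for HASS. No measurement or participant is added. The price is a weaker conclusion from a null result. If a margin is adopted, the sponsor should know that truly identical brands may often fail it: 40% to 61% of the time at n=20 and 62% to 80% at n=15 for the assumed ±0.5 SD.

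### The three-set ANOVA in Section 9 is not a test of brand, because two of its three sets are the same hearing aid, and the brand comparison itself is left undefined

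*Combined protocol and SAP*

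**What the plan says.** Section 2 asks whether users "perceive a difference between Brand A and Brand B devices in their daily life". Section 9 ties the sample size to the same two-way comparison: "Fifteen to twenty participants are needed to determine significant differences between the study set A device and study set B device".

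Section 4 says that "Sets A and C are the same hearing aids but will be different color casings". In the visit table of Section 8, every participant wears Set A in home trial 1 and Set B in home trial 2, and is then "sent home with Set A (Participant is told this is set C) for home trial #3". No randomisation or counterbalancing of order is described.

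Section 9 plans repeated measures ANOVA throughout. For the sound quality questionnaire it says: "The mean scores for each subsection of the sound quality questionnaire will be analyzed between the three test devices for all participants". The next sentence repeats this almost word for word for the three sets of study devices. It then adds: "Repeated measures ANOVA will also be used to determine if there are any individual differences between the brands". That sentence names no score, no contrast and no rule for the two Set A periods. The sentence on the satisfaction survey (HASS) gives no factor levels either. No follow-up comparison or period term is specified.

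**The concern.** A three-level F test asks whether any of the three means differ. Here it has two degrees of freedom. One is Set B against the average of the two Set A periods, which is the brand question. The other is the first Set A period against the last. The aid is the same in both, so any difference reflects time, casing color or label.

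A significant F could therefore be reported as a perceived brand difference when ratings only drifted over the home trials. Spreading the test over two degrees of freedom also costs power for a real brand effect.

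The sentence on brands does not close the gap. An analyst could use Visit 2 only, Visit 4 only, the average of the two, or all three levels, and could choose after seeing the data. A against C is worth having, because it shows how far ratings move when the aid does not change, but it answers a different question.

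**Working it through.** **The plan's own figure.** The 15 to 20 participants in Section 9 (20 in Section 4) cannot be reproduced. The document gives no alpha, power, effect size or SD, and Section 9 says no power analysis was done.

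**Inputs.** From the document: period order A, B, A; n = 15 or 20. Assumed: residual SD of 1 within participants, independent residuals, two-sided alpha 0.05. The sizes of drift and brand effect are also assumed, so a range is shown.

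**Formulas**, with period means μ1, μ2, μ3 in SD units:

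- F test: noncentrality λ = n Σ(μj − mean)², on 2 and 2(n − 1) df. Critical value 3.24 (n = 20) or 3.34 (n = 15).
- Contrast B − (A1 + A3)/2: variance 1 + 1/4 + 1/4 = 1.5; noncentrality √n × [μ2 − (μ1 + μ3)/2]/√1.5, on n − 1 df.
- B against the first Set A period only: noncentrality √n × (μ2 − μ1)/√2, on n − 1 df.

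**1. No brand difference, linear drift d per home trial.** The means are 0, d, 2d, so λ = 2nd². The contrast has mean d − (0 + 2d)/2 = 0.

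| d (SD) | λ, n=20 | F significant, n=20 | λ, n=15 | F significant, n=15 | Contrast significant |
|---|---|---|---|---|---|
| 0.2 | 1.6 | 18% | 1.2 | 14% | 5% |
| 0.3 | 3.6 | 35% | 2.7 | 27% | 5% |
| 0.4 | 6.4 | 58% | 4.8 | 44% | 5% |

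At d = 0.4 and n = 20, comparing Visit 3 with Visit 2 alone is falsely significant in 22%, so how the Set A periods enter matters.

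**2. Real brand effect δ, no drift, n = 20.** The means are 0, δ, 0, so λ = 2nδ²/3.

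| δ (SD) | λ | F test | Contrast | B against first A only |
|---|---|---|---|---|
| 0.565 | 4.26 | 41% | 50% | 40% |
| 0.809 | 8.73 | 72% | 80% | 68% |

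**3. Limits of the contrast, n = 20, no brand difference.**

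- Only home trial 3 shifts, by 0.8 SD. The contrast has mean −0.4 and noncentrality −1.46, and is falsely significant in 28%. For the F test λ = 8.53, giving 71%. A single 0.8 SD step after home trial 1 gives the same two rates.
- Unequal home trials. Section 10 gives only a total: "The expected duration of participation is six weeks". Assume lengths of 2, 3 and 1 weeks and a drift of 0.2 SD per week. Ratings at weeks 2, 5 and 6 then have means 0.4, 1.0 and 1.2. The contrast has mean 1.0 − 0.8 = 0.2 and noncentrality 0.73, giving 11%. For the F test λ = 6.93, giving 61%.

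**4. Precision of the contrast.** The 95% CI half-width is 2.093 × √(1.5/20) = 0.57 SD at n = 20, and 2.145 × √(1.5/15) = 0.68 SD at n = 15.

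**The case against.** Section 9 never calls the three-set ANOVA the brand test, and it has a separate sentence on brands. The documented defect is therefore an under-specified brand analysis, and the misreporting is an inference. This is fair, but that sentence gives no score or contrast, so the three-set comparison is the only one a reader could carry out as written.

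The phrase about three test devices is ambiguous. Own aids are rated at Visit 1, so it could mean own, A and B. The sentence that follows it refers expressly to the three sets of study devices, and the point stands on that.

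The rates of 18% to 58% are rates of a significant F, not of false brand claims. A careful analyst would look further. At n = 20, requiring Set B to differ from both Set A periods in the same direction brings false brand calls to 0.5% or less, at the cost of power (23% where the contrast has 50%). Ordinary Bonferroni follow-up against either period gives about 7%, 12% and 22% at the three drifts. This is right as far as it goes, but Section 9 specifies no follow-up of any kind.

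Drift may also be small. Participants are experienced users, and conditions that cause fluctuating hearing are excluded. No figure follows from this, so the range has to stand as assumed.

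Finally, the fixed order is the root problem, and the contrast cures only linear drift. That is true, and the plan should say so. In both non-linear or unequal-length cases worked here, the contrast was falsely significant far less often than the F test.

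**Conclusion.** The concern holds. Two of the three levels are the same aid, so the three-set F test does not test brand, whatever drift is assumed. The sentence on brands leaves both the score and the handling of the two Set A periods open.

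The size of the problem depends on a drift the document does not give. With independent residuals and alpha 0.05, drifts of 0.2 to 0.4 SD per home trial make the F test significant in 18% to 58% of studies at n = 20, and 14% to 44% at n = 15, with no brand difference. The power lost relative to the contrast is 8 to 9 percentage points in the cases worked.

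The study is exploratory, expects no difference and plans only an internal report, so the consequence is limited. The change is still worth making, because it concerns the stated objective and uses data already planned.

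**What to change.** In Section 9, define the brand test for each questionnaire score as the within-participant contrast of Set B (Visit 3) minus the mean of the two Set A ratings (Visits 2 and 4), with its 95% CI. As no difference is expected, the interval also shows how large a difference remains possible, which a non-significant F does not.

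Report Set A at Visit 2 against the set called C at Visit 4 separately, as the change in ratings when the aid stays the same. Say that it includes time, casing color and label effects.

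State the limits: averaging the two Set A periods removes a linear trend only if the three home trials are about equal in length, and non-linear period effects remain.

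Optionally, name one overall score as the lead result and label subsection and individual HASS results exploratory.

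A minor related point: Section 5 mentions a Net Promoter Score calculation beside the primary endpoint, but Sections 6, 8 and 9 identify no item, visit or analysis for it. The item may sit in the survey, whose questions are not shown. Either delete the mention, or identify the item at Visits 2 to 4 and list it as descriptive in Sections 6 and 9.

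The cost is wording in Sections 5, 6 and 9, and at most one added question per visit. The contrast needs both Set A trials, which the plan already provides for: "Data collection will terminate once the acceptable number of participants has been recruited and have completed all three trials". The downside is that the omnibus F test no longer serves as the brand test.
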